Aim #2: To determine whether teachers can implement the TAPES skills with fidelity/quality. Descriptive statistics will be used to test this aim. We will examine mean scores over time on our fidelity measures (e.g., *S-H Meeting Fidelity and Quality Measure*) to determine the ability of teachers to implement TAPES skills accurately and with high quality. We will also examine which teacher-specific and child-specific variables affect fidelity ratings.

Aim #3 (Primary Outcome): To assess the impact of TAPES, compared to TAT, on teachers' a) *knowledge* regarding student anxiety symptoms and anxiety reduction strategies and b) use of anxiety reduction skills in classroom. To achieve this aim, we will first assess the equivalence of teachers randomized into either TAPES or TAT on baseline teacher (years of experience,

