burnout, teacher efficacy; teacher behavior) and child characteristics (e.g., gender, age, baseline anxiety symptoms, classroom functioning). To test the main hypothesis, that teachers in TAPES, compared to TAT, will have higher knowledge about anxiety reduction, we will examine scores on the *Teacher Knowledge Assessment* at post-training, and at the end of school year as outcomes in GLM controlling for teacher pre-training score. Let y_i denote the post-training or end of school year test score of teacher i, x_{i1} and x_{i2} denote teacher i's group assignment and pre-training test score, respectively, and ε_i denote resident term. Rejecting $\beta_1 \leq 0$ and $\beta_3 \leq 0$ in the model: $y_i = \beta_0 + \beta_1 \times x_{i1} + \beta_2 \times x_{i2} + \beta_3 \times x_{i1} \times x_{i2} + \varepsilon_i$ suggests that TAPES teachers' post-training test scores are higher and they have a greater gain in knowledge than TAT teachers. Teacher-specific covariates can be added to the above model as needed. To test the hypothesis that TAPES, compared to TAT, will result in greater use of anxiety reduction skills in the classroom, IE's Classroom Observation of Teachers Skills rating for each pair of teacher and anxious student at baseline, post-intervention, and 3-month follow-up will be modeled in GLMM. Now rating, y_{ijk} are nested within teacher k and student j, who is nested within teacher k, in the multilevel equations: Level 1: $y_{ijk} = \pi_{0jk} + \pi_{1jk} \times \text{timepoint}_{ijk} + e_{ijk}$; Level 2: $\pi_{0jk} = \beta_{00k} + r_{0jk}$ and $\pi_{1jk} = \beta_{10k} + r_{1jk}$; Level 3: $\beta_{00k} = \gamma_{000} + \gamma_{001} \times w_k + u_{00k}$ and $\beta_{10k} = \gamma_{100} + \gamma_{101} \times w_k + u_{10k}$; where w_k denotes teacher k's intervention-training group assignment with e, r, and u representing error terms in the respective levels. Teacher-specific (e.g., years of teaching experience, teaching efficacy) and child-specific (e.g., age, baseline anxiety severity) covariates can be added to Levels 2 and 3 equations as needed. Aim #4 (Secondary Outcomes): To examine the impact of TAPES relative to TAT on student outcomes. Change scores on student mental health (e.g., Spence Children's Anxiety Scale, SCAS) and academic achievement (e.g., Woodcock-Johnson Tests of Achievement) from pre-to postintervention and 3-month follow-up will be modeled as GLMM similar to above in Aim 3. **Exploratory aims**: To examine mediators (proposed in the theory of change, see Figure 1 in Appendix) and predictors and moderators (e.g. Teacher Background Form, MBI-Educators Scale) of TAPES impact on teacher knowledge and behavior. Structural equation modeling (SEM) will be used to explore potential predictors (e.g., baseline teacher burnout as measured by MBI-ES), mediators (e.g., subscale scores from the OSTES) and moderators (e.g., years of teacher experience) on teacher behavior change (e.g., change score on the Classroom Observation of Teachers Skills at pre-, post-intervention and 3-month follow-up). Sub study: Aim #1: Assess the direct and indirect cost of pediatric anxiety among youth enrolled in the TAPES intervention. This aim involves the modification of existing measures of direct and indirect cost. These measures will be administered to parents and teachers at existing TAPES assessment time points (i.e. baseline, post intervention and three-month follow up). Aim #1a: Estimating the cost of pediatric anxiety through direct and indirect costs. Aim #2: To examine the child and parent benefit of TAPES compared to UC. This aim involves estimating the cost of TAPES relative to the UC condition in relation to direct and indirect costs. Exploratory Aim: To examine family demographic factors as moderators of pediatric anxiety cost. **Power Analysis.** Although this is a development study proposing a small pilot RCT, attempts were made to estimate statistical power for the key outcomes based on existing literatures on similar measures (see White et al., 2011 for Teacher Knowledge Assessment and Barrett et al., 2005 for child anxiety using the SCAS). Using Optimal Design version 3.0 calculations for both variables were based on an anticipated enrollment of 20 teachers in each group (and 1-2 students per teacher). We assumed a conservative within-teacher ICC of 0.10 (Eldridge et al., 2004) and

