
an alpha level was set at .05. Below is a list of minimum effect sizes (calculated as within-group difference in change score, divided by the pooled standard deviation) needed to be detectable with 80% power. With 20 teachers in each group, we will have 80% power to detect the effect size found by White et al. (2011) of d = 1.19 on teacher knowledge. With 30 students in each group, we will have 80% power to detect the effect size found by Barret et al. (2005) of d = .92on child anxiety (effect sizes based on moderately anxious students at pre-post timepoints). Time Table : We are requesting funds for three years. The first six months will be for administrative study start-up tasks (hiring, IRB approval), IE training, and TAPES refinement and review of materials with DT (Stage 1). Months 7 - 20 (Stage 2) will be devoted to recruitment of teachers and students for open trials and further adaptation and refinement of TAPES. Months 21 to 34 will be devoted to implementing the RCT. The final two months (35-36) will be devoted to completing data analyses and manuscript preparation. Personnel: Relevant Expertise of Research Team. The core UCHC research team (Drs. [name] & [name]) along with our consultants have over 20 years of experience in conducting research on the development, evaluation, and dissemination of school-based programs for teachers and school personnel. In addition, the team has extensive experience providing education and training in anxiety reduction skills to school-based and community personnel. Both [name] & [name] moved to UCHC in 2014. In that time they have successfully partnered with 7 CT school districts which now serve as authentic environments for their funded research. They have trained over 40 school clinicians and 17 school nurses as part of their research-exceeding initial recruitment goals. Together they also established the Child/Adolescent Anxiety and Mood Program (CAMP). CAMP conducts community-based research focusing on child and adolescent anxiety and mood disorders, with an emphasis on intervention and dissemination. CAMP now has research coordinators, postdoctoral fellows, and research assistants who work together to recruit research participants and implement studies funded by NIMH and IES. CAMP holds weekly and monthly research meetings that are attended by residents, fellows, and faculty. Currently, CAMP members include 2 faculty, 3 postdocs, 2 Masters level staff, and 8 student research assistants. Finally, Drs. [name] and [name] share responsibility for teaching seminars on child anxiety for psychiatry residents at UCHC. Together, they have given numerous seminars and presentations on childhood anxiety and CBT to a variety of audiences (e.g., parents, teachers, counselors, physicians, and psychiatrists) and have trained school-based clinicians and nurses in the principles and strategies of delivering CBT to anxious youth within schools. These prior experiences have prepared the investigative team to successfully conduct this proposed study. This project reflects a significant and logical next step in this program of research by training teachers in the identification and support of anxious youth. Below is a list of key personnel that will also support this grant, their qualifications, roles, responsibilities, and percent of time and calendar months per year to be devoted to the project are listed below. Evidence of publishing in peer-reviewed scientific journals is documented in the biosketches. Each team member has experience that will ensure the successful implementation of this study.

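### The effects of 1.19 and 0.92 listed as 80%-power minima do not follow from the stated inputs, and their definition does not match the TAPES–TAT comparison

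*Combined protocol and SAP*

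**What the plan says.** The Power Analysis section bases both calculations on an "anticipated enrollment of 20 teachers in each group (and 1-2 students per teacher", with alpha at .05. It adds: "We assumed a conservative within-teacher ICC of 0.10". It then introduces its results as "minimum effect sizes (calculated as within-group difference in change score, divided by the pooled standard deviation) needed to be detectable with 80% power". Two entries follow:

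- Teacher knowledge: "With 20 teachers in each group, we will have 80% power to detect the effect size" of an earlier study, d = 1.19.
- Child anxiety: "With 30 students in each group, we will have 80% power to detect the effect size" of another earlier study, d = 0.92, with the note "effect sizes based on moderately anxious students at pre-post timepoints".

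The tests themselves are between arms. Aim #3 in the Data Analytic Plan is "To assess the impact of TAPES, compared to TAT". Its knowledge model is meant to show that TAPES teachers score higher "and they have a greater gain in knowledge than TAT teachers". Aim #4 makes the same TAPES-to-TAT comparison for students. Under Intervention Conditions, TAT is a 3-hour didactic training on student anxiety, so the comparator is active.

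**The concern.** A minimum detectable effect is fixed by the sample size, the alpha, the power and the variance structure. Here the values described as minima are effects borrowed from the literature, so there is no reason for them to equal the design's 80% limits.

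The definition raises a second question. A within-group change compares a group with its own baseline. The trial compares the change in one trained group with the change in another. If TAT teachers or their students also improve, a one-arm gain overstates the difference to be detected.

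The project is meant to lead to a larger efficacy trial. A reader planning that trial could take 1.19 and 0.92 as this design's 80% limits, or take a one-arm gain as the expected TAPES–TAT difference. The plan supports neither use.

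**Working it through.** **Inputs from the documents.** Alpha 0.05, power 80%, 20 teachers per arm, 1–2 students per teacher, 30 students per arm (30/20 = 1.5 per teacher) and ICC 0.10 come from Power Analysis. Allocation is 1:1 by teacher (Randomization). Sidedness is not stated in Power Analysis; the nulls under Aim #3 are one-sided. No pre-post correlation or SD scale is given.

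**Method.** Noncentral t, with effects in SD units of the analysed score and no covariate adjustment. The minimum is the difference at which power reaches 80%.

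**Teacher knowledge.** SE = √(2/20) = 0.316, df = 38.

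- Minimum: 0.909 two-sided, 0.801 one-sided.
- Power at 1.19: 95.6% two-sided, 98.0% one-sided.
- 1.19 would be the limit with 12–13 teachers per arm: the minimum is 1.197 at 12 and 1.145 at 13.

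**Child anxiety.** SE = √(4[ρ + (1 − ρ)/m]/J), with J = 40 teachers, ρ = 0.10, m students per teacher and df = 38. At m = 1.5, SE = √(4 × 0.70/40) = 0.265.

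| Students per teacher | Minimum, two-sided | Minimum, one-sided | Two-sided power at 0.92 |
|---|---|---|---|
| 1 | 0.909 | 0.801 | 80.9% |
| 1.5 (30 per arm) | 0.761 | 0.670 | 92.3% |
| 2 | 0.674 | 0.594 | 96.9% |

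If half the teachers have one student and half have two, the minimum is 0.766 and power at 0.92 is 92.0%. The value 0.92 would be the limit with about 14 teachers and 21 students per arm (J = 28, minimum 0.920).

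**Gaps.** Teachers: 1.19 − 0.909 = 0.28 SD, or 31% above the minimum. Students: 0.92 − 0.761 = 0.16 SD, or 21% above it; 0.01 SD at one and 0.25 SD at two students per teacher.

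**Attempts to recover the plan's values**

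- *One-sided test:* the minima fall to 0.80 and 0.67, which widens the gap.
- *Stricter alpha:* two-sided 0.01 gives 1.13 for teachers, still below 1.19.
- *Different ICC:* at 30 students per arm, the minimum runs only from 0.742 (ICC 0) to 0.909 (ICC 1).
- *Literal one-arm paired test, SD of change:* 0.660 for 20 teachers and 0.529 for 30 students (0.553 with clustering). On a raw-score SD these are multiplied by √(2(1 − r)), giving at most 0.93 and 0.78 at r = 0.
- *Two-arm change scores on a raw-score SD:* 0.909 × √(2(1 − r)) = 1.19 needs r ≈ 0.14, and 0.761 × √(2(1 − r)) = 0.92 needs r ≈ 0.27.
- *One student per teacher:* almost gives 0.92, but means 20 students per arm and leaves 1.19 unexplained.

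**If within-group is meant literally.** Suppose the listed effect is the TAPES gain and TAT teachers gain g, in the same SD units. The contrast is then 1.19 − g, and power stays at 80% or more only while g ≤ 0.28. For students the limit is g ≤ 0.16 (0.01 at one and 0.25 at two students per teacher). This is illustrative, because the documents give no expected TAT gain.

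**The case against.** - **The sentences may mean at least 80% power.** Read that way they are true, since power is about 96% and 92%. This stands as a limit on the consequence: the trial is not shown to be underpowered. It does not rescue the lead-in, which calls the values minima.
- **An unreported input could explain the figures.** A change-score analysis scaled by a raw-score SD cannot be excluded, because the effect is defined from change scores. It needs correlations of about 0.14 and 0.27, low and different for the two outcomes, and neither is stated. At best the figures cannot be reproduced from what the plan reports.
- **The student figure fits the cautious end of the range.** One student per teacher gives 0.909, and Stage 3: Pilot RCT treats 60 students as a maximum. This is fair, and the 0.16 SD gap applies only at 1.5 students per teacher. But the sentence itself specifies 30 students per group.
- **The recomputed 0.91 is not for the planned model.** Aim #3 uses a GLM with a group-by-pretest interaction, in which the group coefficient is the effect at a pretest score of zero. If the pretest were uncentred with a mean 1 SD from zero (an assumption), the two-sided minimum for that coefficient would be about 1.12 to 1.29 for pre-post correlations from 0.5 to 0. With centring it would be about 0.79 to 0.91. This stands, so 0.91 must be labelled as a simple unadjusted approximation.
- **Within-group may be a one-word slip.** The references to a pooled SD and to each group make that plausible. The cited studies are not available here to settle it, and a slip would still need correcting.

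**Conclusion.** The concern holds. On the stated inputs, the two-sided unadjusted minima are about 0.91 for teacher knowledge and 0.76 for child anxiety (0.67 to 0.91 across two to one students per teacher), not 1.19 and 0.92. None of the alternative readings recovers both listed values without inputs the plan does not state.

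The mislabelling on its own is conservative. The within-group point is conditional: if it is a slip, it needs correcting; if it is literal, the 80% claim does not carry over to the TAPES–TAT contrast to the extent that TAT also produces gains. No loss of power is claimed.

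These figures assume equal arms, full enrolment, no covariate gain and effects in SD units of the analysed score. They are not minima for the interaction GLM or the Aim #4 GLMM. In a small pilot where child anxiety is secondary, the power statement should be corrected; this is not a reason to alter the design.

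**What to change.** Replace the two power sentences with between-arm minimum detectable differences, for example:

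> For a simple unadjusted two-arm comparison of TAPES and TAT at two-sided .05 and 80% power, the minimum detectable difference, in SD units of the analysed score, is about 0.91 for teacher knowledge (20 teachers per arm) and 0.76 for child anxiety (30 students from 20 teachers per arm, ICC 0.10; 0.67 at two students per teacher and 0.91 at one). These are approximations and not minima for the interaction GLM or the GLMM.

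In addition:

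- State the sidedness. If the one-sided nulls of Aim #3 are the basis, give 0.80 and 0.67 (0.59 to 0.80) instead.
- Say whether the SD is of raw or change scores, and give the assumed pre-post correlation if change scores are scaled by a raw-score SD.
- Correct the within-group definition, or say that it is intended.
- Name the comparator behind each published effect. Cite those effects as context, not as 80% minima or as the expected TAPES–TAT difference.

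The cost is two sentences and one definition in Power Analysis, with no extra participants, data or change to the sample size.

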Resources to Conduct the Project. If awarded, the project administration will be housed at UCONN Health (UCHC) which is the state university medical center of Connecticut (CT) located in Farmington (a suburb of Hartford, the capital of CT). UCHC is home to the School of Medicine, School of Dental Medicine, John Dempsey Hospital, UConn Medical Group, and UConn Health Partners (among others). It has a thriving research enterprise which includes several externally funded research centers. UCHC is part of the University of CT system and shares many resources with the Storrs campus (where there is a well-respected School Psychology program and Department of Education). Thus, the current project will be supported by an abundance of resources. The major components of UCHC relevant for this project include: the Department of Psychiatry, Division of Child and Adolescent Psychiatry, Connecticut

Institute for Clinical and Translational Science (CICATS) as well as participating elementary schools which will serve as the implementation sites for this project.

UCHC Department of Psychiatry: This project will be awarded to the Department of Psychiatry (Department), a department with a distinguished history beginning in 1969. The Department provides community psychiatric services as well as consultation clinics, inpatient units, emergency/crisis services, and day hospitals. The Department ranks the highest in external federal funding within the SOM and is home to several federally funded research centers (e.g., Alcohol Research Center). The Division of Child and Adolescent Psychiatry: One of the major components of the Department is the Division of Child and Adolescent Psychiatry (Division) where PIs are faculty members. The Division has administrative, faculty, clinical and research space for all staff. There is also a separate office building (Kane Street Clinic) devoted to clinical and research activities, where the PIs have their office space and research space (see below). The Connecticut Institute for Clinical and Translational Science: CICATS was created in 2009 to transform and improve the way clinical and translational science is conceived, conducted, and disseminated. CICATS is both an academic unit of UCHC, and a partnership of institutions in the region dedicated to advancing clinical and translational research. The overall vision of CICATS is to serve as an engine to expedite and enhance the research, development, testing and implementation of diagnostics and therapeutics across a wide range of human diseases and conditions. CICATS aims to reduce barriers to the development, completion, and dissemination of clinical research-including school based research. The center provides services, support, and consultation in the following areas: education and training, regulatory support, IRB protocols, ethical concerns, legal and policy issues, subject recruitment, data management, data analysis, and study design and conduction. Toward this end, this center will provide support to the PIs as needed in the implementation of this project.

Computing and Office Resources: Computing resources and office space is available to all faculty and support staff for this project. Our research lab includes individual offices for evaluations, a large office suite, a conference room, storage space, and a waiting room (when evaluations are done on site rather than at the school). All offices are equipped with lockable file cabinet storage, telephones with voicemail, and a network printer. Computers are equipped with word processing, database management, bibliographic reference manager, and the statistical software necessary to conduct analyses and prepare manuscripts. Access to a shared drive for sharing files is also available. The space is large enough to house all site staff working on this grant. The Division has an IT administrator that provides support as a key element of the service. Servers provide functions including printing, e-mail and software applications. Network directories are backed up to protected file servers daily. There is also phone support, on-site support and remote control support for desktop PC and network problems. Anti-virus software is run daily on the networks as well. UCHC will provide access to tools (e.g., copying machine, fax, computers, phones) needed for project implementation.

Access, Availability, and Cooperation of Schools and Teachers for this Project: Three CT school districts have agreed to participate in this study (see letters of support). Within these districts there are approximately 26 elementary schools, 460 teachers and 6,000 students. Thus, we will draw from a large pool of teachers. We will randomly select teachers from the volunteer list if more volunteer than needed. For the past two years we have been working with school personnel in seven school districts. We have a strong and positive relationship with these school districts and can recruit more districts if needed.

Resources to Disseminate Results of the Project: Dissemination of research findings has been a core activity of the research team. In the past year alone, the PIs have presented at over 15 national and local venues (including to school personnel and parent organizations), presented 7 posters/talks at national or local conferences, and published 5 peer-reviewed manuscripts (2016 only-see biosketches). Thus, the individual team members have the proven capacity to disseminate research findings. In addition, UCHC has a communications office that regularly requests research from faculty and submits press releases to appropriate public interest sources. Findings from the current pilot study will be disseminated in several ways. We will present findings at national conferences (e.g., NASP; SPR), to CT State Department of Education, and to participating school districts. Audiences that will benefit from this research include state and local school personnel (e.g., administrators, teachers, principals, counselors). Finally, we plan to publish findings in a peer-reviewed journal (e.g., *School Mental Health*) and will have the final iteration of the training and related materials for testing in a large efficacy study.
